whether or not they took their medication. This will allow us to keep track of the stability and magnitude of pain and mood, as well as treatment compliance. To encourage them to keep up with this requirement, each time they submit these answers, they will receive 25 cents. Responses and payments will be logged automatically into a secure database that only study personnel will have access to; if participants miss more than 3 consecutive ratings in a row, research personnel will call or text them to remind them to rate or verify that their app is still working (they are automatically alerted via email by a program designed by the lab). The unblinded monitor designated for this study will check participants ratings bi-weekly to verify that ratings are being completed.

- Follow up: Patients will be asked if they wish to be added to our contact list to participate in future studies of the lab. They will also be asked if they accept to be contacted by phone 3 months and 6 months later to assess the long-term effects of the study intervention on their chronic pain intensity.

5.3 Randomization:

All randomization (and blinding, see next section) will be completed by NUCATS (see study roster in Location 2 for name of personnel). NUCATS will generate two randomization sequences, one for each group (predicted responders, Group A, and non-responders, Group B). This approach will ensure the proper 3:3:1 treatment allocation. We will use a variable block design (size of 5 and size of 10), throughout Phase 2 of the study to minimize temporal bias that can accompany longitudinal scanning studies. We don't anticipate much exclusion after randomization and enrollment based on our previous studies (although screen failures during the run-in are likely due to pain level or pathology lab results, for example). The Phase 2 overall sample size is 210 randomized 3:3:1, therefore n = 90 active treatment (n = 45 responders/non-responders), n = 90 placebo treatment (n = 45 responders/non-responders), and n = 30 no treatment (n = 15 responders/non-responders). We expect an attrition rate of ~33% for a final N = 140.

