8.1.2 Sample Size and Accrual

Statistical power can be estimated based on the Cohen's d effect sizes for differences in pain with 6 weeks of treatment. For responders, based on our preliminary results, we anticipate a mean decrease of 2.5 units on a 0-10 scales with an estimated SD of 3, which results in an effect size estimate of 0.83. In non-responders, the mean decrease in pain is negligible and we do not expect to have enough power to detect this.

Power analyses in G*Power 3.1.3 indicated that we will have ample power to detect pre-to-post changes within a group; with an estimated effect size of $d = 0.8$, power would exceed 95% with a sample of 23 participants. In terms of a between-group comparison, assuming an effect size estimate of $d = 0.8$ across groups, power would exceed 95% for a sample size of $n = 42$ per group. Thus, the total sample size of 210 would provide for adequate power, even accounting for

potential dropout and/or lower-than-expected effect sizes. Assuming that we recruited 70 participants per group, for example, would mean that we could detect between-group effects as small as $d = 0.5$ with power exceeding 80%.

Power analysis for gender: The preliminary gender analyses from phase 1 subjects provide the means to calculate the power necessary for detecting gender effects in placebo propensity. The original sample sizes from phase 1 were based on treating gender and age as covariates of no interest. Based on an anticipated medium-sized effect using Cohen's conventions (Cohen, 1992), calculations in `chi2power` in Stata indicated that for $n=82$ and for $\alpha = 0.05$ we obtain power = 0.31. Instead if we double the number of subjects then we reach adequate detection power: assuming that males have 30% while females 50% placebo incidence rate, for $\alpha = 0.05$ and $n=160$ we obtain just adequate power = 0.74. Therefore all data from phase 1 and 2 will be combined to assess effect of gender on placebo response.

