Our previous fMRI results show that 20 per group should be adequate given the preliminary results and earlier studies. Also, 20 per group allows for 80+% statistical power for effect sizes of 1 SD difference between groups. For DTI and T1 studies our earlier studies indicate that 20/group for within-subject contrasts is adequate but may be just at the limit for whole-brain contrasts for detecting between-group differences. We can overcome this obstacle by using targeted analyses of relevant brain areas. For example, simply removing the cerebellum and occipital cortex voxels from such analyses results in improving on multiple comparison cost by a factor of 2.

The results from Phase 1 affirm the above power calculations. Moreover they indicate that increasing the n for each of the treatment groups by 50% (as proposed in the gender supplement application) can lead to identifying effects that currently remain either non-significant or borderline significant.

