We examine the differences in change in pain for placebo responders versus non-responders and the interaction between active treatment and response type. We can estimate statistical power based on the Cohen's *d* effect sizes for differences in pain with 6-week placebo treatment. For responders, based on our preliminary results, we anticipate a mean decrease of 3 units on a 0-10 scales with an estimated SD of 15, which results in an effect size estimate of 2.0. In non-responders the mean decrease in pain is negligible and we do not expect to have enough power to detect this. Power analyses in G*Power 3.1.3 indicated that we will have ample power. Even with a conservative estimated effect size of $d = 1.0$, power would be 80% for a sample size of $n = 17$ per group which would allow to also detect the interaction effects. In addition, it ensures adequate sample sizes even assuming some attrition in each group. For brain imaging contrasts, fMRI results show that 20 per group should be adequate given the preliminary results and earlier studies. For DTI and T1 studies our earlier studies indicate that 25/group for within subject contrasts is adequate but may be just at the limit for whole-brain contrasts for detecting between-group differences.

Phase 1 results are consistent with above power calculations. They also show that a number of predictors were only borderline significant. Thus, increasing the number of treatment arm subjects by an additional 40 patients would provide opportunity to detect smaller effects and to test for gender dependence of placebo response.

J) Stopping Rules

This study will be stopped prior to its completion if: (1) the intervention is associated with adverse effects that call into question the safety of the intervention; (2) difficulty in study recruitment or retention will significantly impact the ability to evaluate the study endpoints; (3) any new information becomes available during the trial that necessitates stopping the trial; or (4) other situations occur that might warrant stopping the trial.

K) Designation of an Independent Monitor

The Independent Monitor for this study is [name] [name]. [name] is not associated with this research project and thus works independently of the PI, [name]. Since [name] is leaving, we need a new person to do this for us.

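### The 70-per-group power example in 8.1.2 does not describe the planned 3:3:1 design, and the drug-by-predicted-class interaction has no defined power figure

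*Combined protocol and SAP*

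**What the plan says.** Section 2.1.1 lists first the interaction between placebo response and active treatment, by predicted responder class. Section 8.1.1 expects a differential interaction but gives no size for it.

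Section 8.1.2 starts from a 2.5-point fall in responders, "with an estimated SD of 3, which results in an effect size estimate of 0.83". It gives power for a within-group change (n = 23, d = 0.8, above 95%). It then turns to two groups: "In terms of a between-group comparison, assuming an effect size estimate of" 0.8, n = 42 per group gives above 95%. It concludes that 210 is adequate even allowing for dropout and smaller effects, and illustrates: "Assuming that we recruited 70 participants per group, for example, would mean that we could detect between-group effects as small as" 0.5 with power above 80%. It also covers gender and imaging ("20 per group allows for 80+% statistical power for effect sizes of 1 SD difference between groups"). It gives no power for the interaction.

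Section 5.3 sets the randomised numbers: "n = 90 active treatment (n = 45 responders/non-responders), n = 90 placebo treatment (n = 45 responders/non-responders), and n = 30 no treatment". It expects about 33% attrition, leaving 140.

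The Data and Safety Monitoring Plan (DSMP), section I, says that the study examines "the interaction between active treatment and response type". It assumes a 3-point fall "with an estimated SD of 15, which results in an effect size estimate of 2.0", and then states 80% power at d = 1.0 with n = 17 "per group which would allow to also detect the interaction effects".

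Section 8.1.1 randomises 220. It allocates 40 placebo, 40 active and 20 untreated, or 60/60/20 if the Gender Supplement is awarded. The Study Schema, the Study Summary, 5.3 and 8.1.2 all give 210.

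**The concern.** Three equal groups of 70 make 210, so the example appears to assume equal arms and no losses. The design has neither. Because the example directly follows a claim that dropout is covered, a reader will take its figure as the trial's own.

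An interaction contrast has a larger standard error than a two-group difference in the same patients, so two-group power cannot be carried over without stating the interaction effect. If it is carried over, nobody can tell how large an interaction the trial can detect. That bears on the question in 2.1 of whether drug and placebo effects simply add. Section 4.4 also lets recruitment continue until each group is large enough for adequate analysis, which needs a valid target for each contrast.

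**Working it through.** **Inputs.**
- Randomised arms 90/90/30, with 45 per active or placebo cell (5.3).
- Completers 140 of 210: 140 × 3/7 = 60, 60, and 140/7 = 20. With about half predicted responders (8.1.1), that is 30 per active or placebo cell.
- Alpha 0.05 is stated only for the gender calculation and is assumed here. Two-sided testing is also assumed, because it reproduces the plan's figures.

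**Formulas** (noncentral t).
- Two groups: noncentrality = d / √(1/n₁ + 1/n₂), df = n₁ + n₂ − 2.
- Interaction as a difference of differences over four cells of n: noncentrality = δ / √(4/n), df = 4n − 4, with δ in SD units.

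**The plan's figures reproduce.**
- Paired, n = 23, d = 0.8: 95.6%.
- 42 v 42, d = 0.8: 95.2%.
- 70 v 70, d = 0.5: 0.5/√(2/70) = 2.96, power 83.6%.
- 17 v 17, d = 1.0: 80.7% (one-sided would give 88.6%).
- 20 v 20, d = 1.0: 86.9%.

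**The 3:3:1 arms at d = 0.5.**

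| Contrast | Numbers | Noncentrality | Power |
|---|---|---|---|
| Active v placebo, randomised | 90 v 90 | 3.35 | 91.6% |
| Active v placebo, completing | 60 v 60 | 2.74 | 77.5% |
| Either v no treatment, randomised | 90 v 30 | 2.37 | 65.3% |
| Either v no treatment, completing | 60 v 20 | 1.94 | 48.1% |

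At d = 0.8, active v placebo has 99.1% on completing and over 99.9% on randomised numbers; the comparison with no treatment has 86.4% and 96.4%.

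**The DSMP sentence.** With 17 per cell, √(4/17) = 0.485. If δ = 1.0 SD, power is 53%. If δ = 2.0 SD, it is 98%. The DSMP does not say which is meant.

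**Interaction on the planned cells**, for continuous pain change and 50:50 strata.

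| δ (SD) | 30 per cell | 45 per cell |
|---|---|---|
| 1.0 | 77.5% | 91.6% |
| 0.8 | 58.4% | 76.1% |
| 0.5 | 27.4% | 38.5% |

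Eighty per cent power needs δ = 1.03 SD with 30 per cell and 0.84 SD with 45. At SD 3 that is 3.1 and 2.5 points, against a total expected fall of 2.5 points in responders. A 60:40 split of the strata changes little: 56.7% to 74.4% at 0.8 SD.

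**Inputs across sections.** 8.1.2: 2.5/3 = 0.83, as stated. DSMP: 3/15 = 0.2, not 2.0; 3/1.5 = 2.0.

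**Totals in 8.1.1.** 40 + 40 + 20 = 100 and 60 + 60 + 20 = 140. Neither equals 220, and neither is 90/90/30.

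**The case against.** The 70-per-group sentence is offered as an example and speaks of recruited patients. On recruited numbers active v placebo has 92%, so for that contrast its claim is met. The completer shortfall is small: 64 per arm would give 80%, against 60 expected. Section 4.3 keeps data up to withdrawal and 4.4 proposes a likelihood-based mixed model, so 78% is a lower bound if partial data are used. The gain cannot be quantified, because no correlation is given and the equation in 4.4 has no treatment term. Seventy is also 140/2, the two predicted classes at completion, but the text says recruited, and 105 per class are recruited. Nor does 8.1.2 claim d = 0.5 specifically against no treatment. All of this stands. It narrows the point, but the example still fits no planned arm.

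A reader might infer that the DSMP's n = 17 is simply wrong, with true power 53%. The documents do not support that: 53% follows only if d = 1.0 means a difference of differences of 1.0 SD, and the sentence holds at 2.0 SD. The fault is the missing definition.

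A reader might also infer that the primary objective is unpowered. Section 2.1.1 lists the interaction first, but the Study Summary calls it additional and 8.2 counts it among secondary aims. Section 1.2 says that primary outcomes are brain parameters, and the hypothesis in 2.1.1 begins with brain properties. Neither rank nor outcome is settled, so pain change is an assumption here, though 8.1.2 does frame power in pain.

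The SD of 15 may be a lost decimal point for 1.5. The division then works, but 2.0 still conflicts with 0.83.

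**Conclusion.** The concern holds in limited form. The power figure in the 70-per-group example is not what 3:3:1 allocation with one-third attrition delivers. At d = 0.5 it is missed narrowly for active v placebo among completers (78%) and clearly for comparisons with no treatment (65% randomised, 48% completing). The interaction has no power in 8.1.2 and only an undefined claim in the DSMP. The planned cells give 78–92% at 1.0 SD, 58–76% at 0.8 and 27–39% at 0.5.

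These figures rest on two-sided 0.05, continuous pain change rather than the 20% or permutation responder definition in 2.3.1, 50:50 strata, and assumed interaction sizes, because the documents give none.

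They do not show that the trial as a whole is underpowered: active v placebo keeps 99% or more at d = 0.8. It is also tempting to read 60/60/20 in 8.1.1 as completers mislabelled as randomised, since it totals 140. The text ties it to the Gender Supplement and gives 40/40/20 as the base, so that reading is a guess. What is certain is that these numbers, 220, 210 and 90/90/30 do not agree.

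**What to change.** - **8.1.2:** replace the 70-per-group example with power on the planned arms and cells, for randomised and completing numbers, covering active v placebo, placebo v no treatment, and the interaction. Define the interaction effect, label its size as an assumption, and state that the outcome is continuous pain change.
- **DSMP section I:** limit n = 17 to the two-group comparison, or define the interaction effect size for which it holds.
- **Both:** use one mean and one SD.
- **8.1.1:** reconcile 220 with 210, and 40/40/20 and 60/60/20 with 90/90/30, saying whether each is randomised or completing.

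These are text changes with no added patients and no redesign. Their cost is that stated power becomes less favourable.

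Separately, the Study Summary, 2.1.1 and 8.2 must agree on the rank of the interaction. Which rank is right is the sponsor's decision, and it is more than an edit. Reporting the interaction with a 95% confidence interval, and illustrating the effect of misclassifying predicted responders, would be useful but optional.

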Objectives	The overall purpose of Phase 1 was to identify brain mechanisms and behavioral markers of placebo analgesia propensity in chronic back pain patients. The markers identified in that phase will now be used in Phase 2 to predict placebo propensity in a separate cohort of chronic back pain patients and in turn, validate the markers' reliability to detect response. An additional objective of Phase 2 is to study the interaction of placebo propensity with active treatment.
Number of Subjects	A total of 340 participants will be enrolled across both phases. Phase 1 will have an expected enrollment of 130 participants to attain 64 completed participants Phase 2 will have an expected enrollment of 210 participants to attain 140 completed participants.
Diagnosis and Main Inclusion Criteria	Chronic back pain (history of low back pain for a minimum of 6 months with or without signs and symptoms of radiculopathy)
Study Product(s), Dose, Route, Regimen	Naproxen, 500mg, po and Omeprazole, 20 mg, po, and matching placebo capsules, all po bid
Duration of administration	6 weeks total for Phase 2 for all study products and treatments
Active Treatment	1 capsule Naproxen (500mg) /1 capsule Omeprazole (20 mg), both oral b.i.d.
Statistical Methodology	Brain activity contrasts are done as a two-way (treatment groups) repeated measures (time: start vs. end) ANOVA (two-way repeated measures-ANOVA). For responders, based on our preliminary results, we anticipate a mean decrease of 2.5 units on a 0-10 scales with an estimated SD of 3. Thus, the estimated Cohen's d effect size across time is an effect size estimate of 0.83.

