2.3 Endpoints

- 2.3.1 Endpoint for primary objective: (1) Placebo response (defined as > 20% reduction in pain intensity following placebo treatment, or defined from pain app ratings using permutation with 0.05 p-value cut-off) versus active treatment response (reduction in pain intensity following naproxen/omeprazole treatment)
- 2.3.2 Endpoints for secondary objective: (1) Testing the specificity and sensitivity of the brain and behavioral parameters from Phase 1, in combination with the TOPPP developed from the study interviews, as predictive markers for response in Phase 2. These parameters will be considered validated if together are at least 80% accurate in stratifying responders from non-responders.
- 2.3.3 Endpoint for gender objective: (1) Testing for females showing higher incidence of placebo response using combined outcomes from phase 1 and phase 2 data.

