8.0 STATISTICAL CONSIDERATIONS

8.1 Summaries of Design, Endpoints, and Analysis

8.1.1 Phase II: Study Design/Study Endpoints

Enroll and randomize 220 CBP patients into the study. Stratify into placebo responders and non-responders based on brain scan results at entry. We anticipate that about 50% of the patients will be placebo responders. All participants are randomized so that 40 receive placebo treatment, 40 active medication, and 20 no treatment. If Gender Supplement is awarded then randomization is slightly different: 60 receive placebo, 60 active medication, and 20 no treatment.

We assume that placebo responders and non-responders will show differential interaction with active medication treatment. We also expect to distinguish the four groups based on brain activity at the end of the trial, and show close correspondence between predicted and actual outcomes regarding placebo responses. Additionally, placebo non-responders should show a robust medication response, especially in comparison to the placebo non-responders receiving placebo treatment. Brain activity contrasts are done as a two-way (treatment groups) repeated measures (time: start vs. end) ANOVA (2RM-ANOVA). This is the procedure we implemented recently in a longitudinal neuroimaging study of pain chronification (Baliki et al., 2012). Post-hoc comparisons then reveal: 1) A contrast of brain activity at end of treatment between placebo non-responders with and without medication treatment to identify brain activity for bottom-up modulation of chronic pain. 2) Brain regions related to chronic pain are identified as areas commonly decreased with placebo treatment for placebo responders and medication treatment for placebo non-responders. 3) Top-down placebo and bottom-up medication effects are distinguished by identifying regions that distinctly increase in activity for placebo and medication treatments based on contrasts for the same groups. 4) The no treatment group brain activity is used as a higher-level contrast, which effectively corrects for this confound.

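### Gender power in 8.1.2: 0.31 at n=82 does not follow from its stated basis, doubling n does not lead from it to 0.74, and the 160 participants behind 0.74 are not identified

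*Combined protocol and SAP*

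**What the plan says.** The gender paragraph of 8.1.2 gives two powers at alpha 0.05, computed with a chi-square power routine.

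- The first, at n=82, is introduced with "Based on an anticipated medium-sized effect" by Cohen's conventions. It leads straight to the second: "we obtain power = 0.31. Instead if we double the number of subjects then we reach adequate detection power".
- The second, at n=160, rests on a separately stated effect, "assuming that males have 30% while females 50% placebo incidence rate", and ends: "we obtain just adequate power = 0.74. Therefore all data from phase 1 and 2 will be combined".

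The gender endpoint in 2.3.3 is "Testing for females showing higher incidence of placebo response using combined outcomes from phase 1 and phase 2 data". Section 2.3.1 defines placebo response by a "reduction in pain intensity following placebo treatment" (or by a permutation test on app ratings).

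On numbers, the Study Summary says "Phase 1 will have an expected enrollment of 130 participants to attain 64 completed participants", without an arm split. With the gender supplement, 8.1.1 allocates Phase 2 as "60 receive placebo, 60 active medication, and 20 no treatment". Section 5.3 randomises 90 to placebo and expects about 33% attrition, to 140 completers overall.

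**The concern.** The contrast between 0.31 and 0.74 is the printed argument for pooling the two phases. It reads as a sample-size effect, but the sentence changes the effect size as well as n. The first figure also looks far too low for a medium effect.

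Separately, neither 82 nor 160 is a participant count printed elsewhere in the plan, and nothing says which arms, which phases or what completion status make up the 160. The endpoint is a rate of response to placebo, so who is counted decides both the power and what the rate measures. If naproxen-treated or untreated patients were needed to reach 160, the result would no longer be a placebo-response rate. Section 2.1.1 uses the no-treatment patients as a negative control.

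**Working it through.** **Inputs.** Alpha 0.05, n=82 with power 0.31, n=160 with power 0.74, and 30% versus 50% (8.1.2); 130 enrolled and 64 completers in Phase 1 (Study Summary); Phase 2 allocation (8.1.1, 5.3). Assumed because not printed: two-sided 2x2 test (1 df), equal genders, and Cohen's medium value taken as w=0.3 or h=0.5.

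**Formulas.**
- Two proportions, m per gender: power = Φ[(0.20 − 1.96·√(0.40·0.60·2/m)) / √((0.30·0.70 + 0.50·0.50)/m)].
- Chi-square, 1 df: power ≈ Φ(w√n − 1.96).

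**Step 1: the 0.74.** With m=80: (0.20 − 1.96·0.0775)/0.0758 = 0.635, and Φ = 0.737. The stated 0.74 reproduces.

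**Step 2: the 0.31 at n=82.**
- w=0.3: 0.3·√82 = 2.717; Φ(0.757) = 0.775.
- h=0.5, equal genders: 0.5·√(41/2) = 2.264; Φ(0.304) = 0.619.
- 30% versus 50%, m=41: (0.20 − 1.96·0.1082)/0.1059 = −0.114; Φ = 0.455.
- 30% versus 50% with a continuity correction gives 0.37, by Fisher's exact test 0.39, and one-sided 0.58.

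None of these gives 0.31.

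**Step 3: does doubling link the two figures?**
- Solving for 0.31 at n=82 gives w=0.162. At n=160 that effect gives Φ(0.162·√160 − 1.96), about 0.53.
- Solving for 0.74 at n=160 gives w=0.206. At n=82 that effect gives 0.46.
- Unequal genders do not help. With 30% versus 50%, 0.31 at n=82 needs a male share of about 22% or 83%, and those splits give 0.55 or 0.52 at n=160.

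**Step 4: who could the 160 be?** I read the 60/60/20 allocation in 8.1.1 as completers, because it sums to the 140 completers planned and 90·(140/210) = 60. Power is for 30% versus 50% with equal genders.

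| Set | n | Power |
|---|---|---|
| Placebo-treated planned completers | at most 64+60 = 124 | at most 0.63 |
| All arms, no-supplement allocation (40+40+20) | 64+100 = 164 | 0.75 |
| All arms, supplement allocation | 64+140 = 204 | 0.84 |
| If 82 is the Phase 1 placebo-treated number (assumption) | 82+60 = 142 to 82+90 = 172 | 0.69 to 0.77 |

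The 124 requires every Phase 1 completer to have had placebo. With 30% or 70% male, power at 124 is 0.54 or 0.57. To reach 160 placebo-treated participants, Phase 1 would have to supply 160−60 = 100, or 160−90 = 70 if all those randomised to placebo in Phase 2 are analysed.

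**The case against.** The 0.74 states its own inputs and reproduces. The sentence names its own rates, so the text never expressly says that the two figures share an effect size. Pooling is prespecified in 2.3.3, 8.1.2 and 8.2 and does not depend on 0.31: at 0.46, n=82 would still be too small. All of this stands.

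The inputs to 0.31 are not printed either. One numerical match exists: the 30% versus 50% effect (w=0.204) with 3 df gives 0.31 at n=82. But a gender-by-response table has 1 df, w=0.204 is not a medium effect, and 3 df gives only 0.57 at n=160. The safe statement is that 0.31 cannot be reproduced from its stated basis.

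The shortfall at 124 can also be challenged. Section 4.3 includes data up to withdrawal, so the documents do not confine the comparison to completers. Section 4.4 allows extra recruitment, and 82 may itself be a Phase 1 count above 64. A reader might infer a ceiling of 90+64 = 154 with power 0.72. That mixes Phase 2 randomised patients with Phase 1 completers. The like-for-like total of printed counts is 90+130 = 220 (power 0.86), which is not a realistic set because the Phase 1 arm split is not given, but it shows that 154 is not a bound.

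Finally, propensity in 2.1.3 might mean the class predicted by Equation 1, which exists in all arms. That is a prediction, whereas 2.3.3 and 8.2 refer to placebo response.

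**Conclusion.** Two points hold.

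First, 0.31 at n=82 does not follow from a medium effect in a 2x2 test (0.62 to 0.78) or from 30% versus 50% (0.46, equal genders). No single effect size gives both 0.31 at n=82 and 0.74 at n=160. This rests only on the conventional medium values and a 1-df test.

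Second, the 160 is undefined. On the plan's definition of placebo response, planned placebo-treated completers reach at most 124 and power at most about 0.63. Planned completer totals pass 160 only by counting naproxen-treated or untreated patients. This part is conditional: with non-completers analysed, or more than 64 placebo-treated patients from Phase 1, 0.74 may be attainable.

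A reader might go further and infer that 0.74 is miscalculated, that the gender objective is certainly underpowered, or that the plan intends to count patients not given placebo. The documents support none of these. The 0.74 reproduces, the Phase 1 placebo-treated number is missing, and no section assigns the other arms to this analysis.

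**What to change.** - In 8.1.2, replace 0.31 with the power at n=82 for the same 30% versus 50% effect (about 0.46 with equal genders), or delete it, so that both figures share one effect size. State the gender split assumed.
- In 2.3.3 and 8.1.2, state that the gender comparison of observed placebo response uses placebo-treated participants only, from both phases, and whether it is limited to completers.
- Give the actual Phase 1 placebo-treated count and restate n and power for that set: about 0.63 or less if limited to planned completers. Do not print 0.72 at n=154 as a ceiling.
- If the Equation 1 class is also compared by gender across all arms, list that as a separate analysis with its own n.

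The cost is text only, with no extra patients, visits or assessments. The stated power may become less favourable.
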